##### ***8.6.4 Baseline Clinical Evaluations***

Descriptive statistics will be provided for the Screening and Baseline data of PASI and IGA.

##### ***8.6.5 Dosing Compliance***

Subjects will be instructed to take the test article twice daily for 12 weeks so that the expected number of doses will be 168 (or 167 for subjects for whom only the evening dose (after 4PM) is taken on Day 1). Dosing compliance (percent of expected doses) =  $100 \times [(reported\ number\ of\ doses) / (expected\ number\ of\ doses)]$ . Reported number of doses will be calculated from the difference between the number of pills in the bottle dispensed and collected. Compliance will be reported as unknown for any subjects who do not return any study drug bottles. Descriptive statistics will be provided for dosing compliance.

Subjects who take at least 80% of the expected total number of doses and have no other evidence of material dosing non-compliance will be considered to be compliant with test article dosing. The number and percent of compliant subjects will be presented.

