- If the subject chose to take the test article in the clinic, administer the morning dose of test article to the subject.
- Record dosing time. Note: dosing time can be obtained verbally from the subject, from the Subject Instruction Sheet, or from administration in the clinic.
- Collect blood for blood biomarker analysis (metabolite analysis, RASP ELISAs, and cytokines) **between 2 and 4 hours after** test article administration (see Section 12.3).
- Collect blood and urine samples for clinical laboratory tests (chemistry, hematology, and urinalysis). If possible, subjects should be fasting for approximately 8 hours.
- Collect urine sample for urine drug metabolism analysis **between 2 and 4 hours after** test article administration (see Section 12.4).
- Perform a UPT for all WOCBP. The result must be negative for the subject to continue dosing with test article.
- Document any AEs.

- Schedule the next visit.

### 9.5 Visit 5 (Day 57 ± 3): Week 8

**One day prior to the visit, the site staff will contact the subject to remind them to note the time of dosing in the Subject Instruction Sheet if the subject chooses to take the morning dose of test article on the day of their clinic visit at home and to inform them that if the subject chooses to take the morning dose of test article in the clinic, the subject will need to remain in the clinic for 1 hour after dosing.**

*At this visit, the investigator or designee will:*

- Query the subject for any changes in health status since the previous visit, including concomitant medications and concurrent procedures/therapies, and document the findings.
- Measure vital signs (see Section 10.7.1).
- Have the subject perform the subject evaluation (PGIC). See Section 10.6.
- Perform clinical evaluations (IGA first, then BSA and PASI). See Section 10.3, Section 10.5, and Section 10.4, respectively.
- Perform a targeted physical exam (see Section 10.7.2). Record any new or worsening clinically significant abnormalities as AEs.
- Perform ECG (see Section 10.7.3).
- Review compliance.
- Document Test Article Accountability; all test articles will be collected and tablets will be counted.
- If the subject chose to take the test article in the clinic, administer the morning dose of test article to the subject.
- Record dosing time. Note: dosing time can be obtained verbally from the subject, from the Subject Instruction Sheet, or from administration in the clinic.

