## 12. LABORATORY TESTS

### 12.1 Blood Chemistries, Hematology, and Urinalysis

Blood and urine specimens will be collected at every clinic visit for chemistry, hematology, and urinalysis. At Visit 1/Screening, serology will be performed for HIV, hepatitis B, and hepatitis C (i.e., HepB-sAg and Hep C-Ab) in all subjects and FSH levels will be evaluated in all females. The post-menopausal range for FSH will be based on the central laboratory's range [typically  $\geq 40$  IU/L]. Subjects must be fasting (approximately 8 hours) for Visit 1/Screening and, if possible, for all post-Screening visits. If fasting samples cannot be collected at the time of other Visit 1/Screening procedures, the subject may return to the clinic for sample collection such that the results of the clinical laboratory tests are available for review prior to Visit 2/Baseline; such testing will still be considered "Visit 1/Screening" labs. If a subject arrives at the clinic for any post-Screening visit without fasting for at least 8 hours, laboratory specimens may be collected as non-fasting, at the discretion of the investigator, and with the appropriate fasting status documented on the lab requisition form.

The following laboratory tests will be performed:

LABORATORY TESTS		
Chemistries	Hematology	Urinalysis
Albumin	Hemoglobin	Color
Alkaline phosphatase	Hematocrit	Appearance/Clarity
ALT (SGPT)	MCV	Albumin
AST (SGOT)	MCH	Creatinine
Bilirubin, total	MCHC	Bilirubin
Calcium	RBC (Erythrocytes)	Blood
Carbon Dioxide §	WBC (Leucocytes)	Glucose
Chloride	RDW	Ketones
Creatinine	Differential count	Leukocyte Esterase
GGT	Basophils	Nitrite
Glucose (fasting)	Eosinophils	pH

LABORATORY TESTS		
Chemistries	Hematology	Urinalysis
LDH	Lymphocytes	Protein
Phosphate	Monocytes	Specific gravity
Potassium	Neutrophils	Urobilinogen
Protein, total	Platelets	Microscopic analysis (if needed)
Sodium		Microalbumin/Creatinine Ratio*
Urea (BUN)		
Uric acid		
eGFR*		
Lipid Panel		
Cholesterol, total		
HDL		
Direct LDL		
Triglycerides		

§ Bicarbonate may be substituted if the participating lab does not perform assay for carbon dioxide.

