### 14.3 Subject Stopping Rules

Safety and tolerability data will be reviewed on an ongoing basis by the Medical Monitor and stopping rules will be applicable starting with dosing of the first subject.

Subjects will be discontinued from dosing, but will continue to be followed in the trial, if any of the following occurs:

- $\geq$  Grade 3 (Common Terminology Criteria for Adverse Events [CTCAE] v5.0) AE or clinically significant laboratory abnormality OR  $\geq$  Grade 2 (CTCAE v5.0) AE (or Grade 3 if a qualified subject is enrolled at Baseline with Grade 2 findings) for the system organ classes (SOCs) of cardiac disorders and/or blood and lymphatic disorders, considered related to trial drug. Any clinically significant laboratory or ECG abnormalities that may trigger a subject stopping rule must be repeated promptly to ensure accuracy and confirm the event meets stopping rule requirements.
- Severe anaphylactic reaction, including bronchospasm;

- Moderate to severe renal impairment, defined as an eGFR  $\leq 50$  mL/min/1.73m^2;  
**Note:** Dosing will be suspended until eGFR exceeds 50 mL/min/1.73m^2 for at least 2 consecutive measurements within 24 hours, at which time dosing may be resumed. A subject with out-of-range value(s) may be re-tested once before dosing is discontinued. Re-testing must occur promptly of an abnormal laboratory value(s).
- Requirement for hemodialysis; and/or
- Significant hepatic impairment, defined as an ALT or AST level  $> 3$  times the upper limit of normal (ULN) or a total bilirubin  $> 2$  times the ULN for more than 24 hours, confirmed on re-testing.  
**Note:** A subject with out-of-range value(s) may be re-tested once before dosing is discontinued. Re-testing must occur promptly of an abnormal laboratory value(s).  
Subjects will be monitored until the AEs resolve or stabilize.

In the event that any of the following are encountered, the Medical Monitor will determine if the trial must stop enrollment:

- SAE considered related to trial drug;
- $\geq$  Grade 3 (CTCAE v5.0) reaction considered related to trial drug;
- $\geq 2$  subjects are discontinued from treatment for safety reasons pertaining to trial drug; and/or
- $\geq 2$  subjects experience similar SAEs or Grade 3 (CTCAE v5.0) AEs related to trial drug.

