#### **14.6 Pregnancy**

WOCBP (see Schedule of Events for definition of WOCBP) must have a UPT prior to trial enrollment. Post-menopausal status must also be confirmed with FSH test results from Visit 1/Screening. Prior to trial enrollment, WOCBP must be advised of the importance of avoiding pregnancy during the trial and the potential risk factors for an unintentional pregnancy. The subject must sign an informed consent form documenting this discussion.

WOCBP should be instructed to contact the investigator immediately if they suspect they might be pregnant (e.g., missed or late menstrual period). If a subject or investigator suspects that a subject may be pregnant at any time during the trial, the test article must be withheld until the results of laboratory pregnancy testing are available. If pregnancy is confirmed, the subject must not receive or administer further test article and must be discontinued from the trial unless the Medical Monitor elects to retain the subject for all or part of the remaining trial period to follow the subject for safety.

If following initiation of trial treatment, it is subsequently discovered that a subject was pregnant or may have been pregnant at the time of test article exposure, the investigator must immediately notify the Medical Monitor and record the pregnancy on the appropriate pregnancy surveillance form. The form will be sent to TI. The investigator will also report

any pregnancy associated with the trial treatment as required by their IRB and keep careful source documentation of the event.

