#### **A 1.5 Dose Modifications**

The subject should not modify the treatment regimen without consultation with the investigator. In the event that the investigator believes that dose modification is necessary (e.g., problems with tolerance), the subject's care should be discussed with the Medical Monitor prior to making any dose modifications. All dose modifications must be reported on the appropriate eCRF.

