#### **A 1.6 Documentation of Administration and Compliance**

The date of the first and final dose of the test article will be recorded on the appropriate eCRF. An eCRF will also be used to record any changes from the dosing specified in the protocol (e.g., investigator directed reduction in dosing frequency or drug holiday).

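### Dosing compliance divides by the full planned course for every subject, so a fully adherent subject directed to stop on or before Day 67 is not counted as compliant

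*SAP*

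**What the plan says.** SAP 8.6.5 sets the denominator: "the expected number of doses will be 168 (or 167 for subjects for whom only the evening dose (after 4PM) is taken" on Day 1). The numerator is tablets dispensed minus tablets collected. "Subjects who take at least 80% of the expected total number of doses", with no other material non-compliance, are counted as compliant. Both descriptive statistics of percent compliance and the number and percent of compliant subjects are planned outputs. The one exception is that compliance is reported as unknown if no bottles come back. Protocol 17.3.3.2 has the same 80% rule but does not say how expected doses are counted. SAP section 9 lists no changes to the protocol's analyses.

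The protocol foresees several situations in which planned doses are not due:

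- **Stopping rules (Protocol 14.3).** "Subjects will be discontinued from dosing, but will continue to be followed in the trial, if any of the following occurs". The renal rule in the same section also allows suspension and resumption.
- **Pregnancy tests (Protocol 9.4 and 9.5).** "The result must be negative for the subject to continue dosing with test article". Under Protocol 14.6, test article is withheld while pregnancy is suspected, and once it is confirmed "the subject must not receive or administer further test article".
- **Investigator-directed changes (Protocol A 1.5 and A 1.6).** "All dose modifications must be reported on the appropriate eCRF", and the example given for the dosing-change eCRF is "investigator directed reduction in dosing frequency or drug holiday".

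**The concern.** A compliance measure should show whether subjects took the doses they were supposed to take. With a fixed denominator, doses that a subject was told not to take count as missed. A subject who follows every instruction can therefore score the same as one who skipped tablets. The clause on other evidence of non-compliance is joined to the 80% rule by *and*. It can only remove subjects from the compliant count, so it cannot restore a subject who falls below 80% for this reason.

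The SAP already accepts the principle in one case: the 167 figure removes a single Day 1 dose that was not due. A directed stop after the Day 29 morning dose leaves 168 − 57 = 111 such doses in the denominator.

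At stake is how one planned table reads. In a trial described as primarily about safety and tolerability, a safety stop would appear there as an adherence failure.

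**Working it through.** **Inputs.** Twice-daily dosing for 12 weeks, denominators 168 and 167, and the 80% threshold (SAP 8.6.5). Visit 4 at Day 29 ± 3, Visit 5 at Day 57 ± 3 and Visit 6 at Day 85 ± 3 (Protocol section 9). About 10 subjects (SAP 8.4). All results assume that every bottle is returned and that tablet counts equal doses taken.

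**Reproducing the plan's figure.** 12 × 7 × 2 = 168. With an evening-only Day 1, 1 + 83 × 2 = 167. Both match.

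**Doses needed to be compliant.** 0.80 × 168 = 134.4, so 135 doses. 0.80 × 167 = 133.6, so 134 doses.

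**Doses taken by a fully adherent subject.** If the last dose is on Day d, the count is 2(d − 1) + 1 when it is the morning dose and 2d when it is the evening dose, less 1 for an evening start.

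| Last dose taken | Of 168 | Of 167 (evening start) | Counted as compliant? |
|---|---|---|---|
| Day 29 morning | 57 = 33.9% | 56 = 33.5% | No |
| Day 57 morning | 113 = 67.3% | 112 = 67.1% | No |
| Day 67 evening | 134 = 79.8% | 133 = 79.6% | No |
| Day 68 morning | 135 = 80.4% | 134 = 80.2% | Yes |

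Across the visit windows (denominator 168), a stop after the Visit 4 morning dose gives 51/168 = 30.4% (Day 26) to 63/168 = 37.5% (Day 32). After the Visit 5 morning dose it gives 107/168 = 63.7% (Day 54) to 119/168 = 70.8% (Day 60).

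**When a directed stop is likely to fall.** Protocol 12.1 says "Blood and urine specimens will be collected at every clinic visit for chemistry, hematology, and urinalysis". Between the first dose and end of treatment, the only scheduled clinic visits are Visits 4 and 5, which also carry the ECGs and pregnancy tests. Suppose a permanent stop follows within 7 days of the visit that triggered it. This is an assumption; Protocol 14.3 says only that repeat testing must be prompt. The latest such stop is then Day 60 + 7 = Day 67, so every stop triggered at these visits falls below 80%.

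**Directed reduction.** The documents give no reduced frequency; assume once daily, with every directed dose taken through Day 84. From Day 51: 2 × 50 + 34 = 134, or 79.8%, not counted. From Day 52: 2 × 51 + 33 = 135, or 80.4%, counted. From Day 29: 56 + 56 = 112, or 66.7%.

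**Temporary suspension.** To fall to 134 doses, an otherwise perfect subject must lose 168 − 134 = 34 doses, or 17 days. The documents do not show that the renal suspension or the pregnancy-test hold would last that long, so short suspensions lower the percentage without changing the flag.

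**Effect on the summaries at N = 10.** Each affected subject moves percent compliant by 1/10 = 10 points. With the other nine at 100%, one Day 29 stop gives a mean of (900 + 33.9)/10 = 93.4%, and one Day 57 stop gives (900 + 67.3)/10 = 96.7%.

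**With a per-subject denominator.** Full adherence scores 100% at any directed stop: for example 57/57 in place of 57/168, or 134/134 in place of 134/168.

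**A smaller related point.** Subjects are told to dose until the next clinic visit, but the denominator assumes exactly 84 days. A completer who takes a Day 85 morning dose scores 169/168 = 100.6%. Over the Visit 6 window the 135-dose cut equals between 135/175 = 77.1% (Day 88, that morning's dose counted) and 135/162 = 83.3% (Day 82, not counted) of the doses available.

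**The case against.** The strongest reply is that this is a convention rather than an error. The SAP rule is complete and reproducible, nothing in the documents contradicts it, and expected total doses can naturally be read as the whole course. Percent of planned doses is also informative in a tolerability trial, because a doses-due measure gives 100% to someone stopped in week 2. That is a good reason to report the planned-course figure, but not to label it compliance: SAP 8.8.1 already summarises exposure separately, and the 167 rule already drops a dose that was not due.

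Second, nothing depends on the flag. The Safety population is the only analysis set. Exposure categories (SAP 8.8.1), AE outputs (SAP 8.8.3) and subject listings (SAP 8.1) would let a reader recognise a directed stop among about 10 subjects. This stands and keeps the severity low. Withdrawal reasons (SAP 8.5) help less, because a subject stopped under Protocol 14.3 remains in the trial.

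Third, the problem arises only if someone is directed to stop. Protocol section 1 reports no interruption or discontinuation among the 41 + 23 = 64 Phase 1 subjects given drug. This also stands, although that dosing lasted at most 10 days and says little about 12 weeks.

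Fourth, the data needed may not be complete. The protocol says that dosing changes and the final dose date go on eCRFs, but does not say that the date and initiator of every stop are recorded. This is a fair caution about the cost of the fix.

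**Conclusion.** The concern holds. As written, SAP 8.6.5 does not count as compliant a subject who took every dose due but was directed to stop on or before Day 67. The cut-off is the same for both denominators (79.8% and 79.6% through Day 67; 80.4% and 80.2% with the Day 68 morning dose). The result rests on returned bottles and accurate tablet counts. The further statement that any stop triggered at Visit 4 or 5 falls below the cut rests on the assumed 7 days.

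The consequence is small: 10 points in percent compliant per affected subject at N = 10, in one descriptive table, and only if such a stop occurs. No efficacy or safety conclusion changes. This is an optional clarification, worth making because it is cheap and corrects a planned output.

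**What to change.** In SAP 8.6.5:

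1. Define expected doses per subject as the doses due over the planned treatment period, excluding those not due because dosing was stopped, suspended, withheld or reduced under the protocol or by investigator direction. Apply the 80% rule to that number.
2. Do not end the period at the last dose taken, so that a subject who stops unprompted is still counted as missing doses.
3. Report percent of the planned 168 (or 167) doses separately, with extent of exposure in SAP 8.8.1.
4. State how voluntary withdrawal from the trial is handled, for example by showing both figures and naming in advance which one enters the compliant count.
5. State whether a Visit 6 morning dose is counted, use the actual Visit 6 date, and treat numerator and denominator alike.

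Protocol 17.3.3.2 does not fix the denominator, so no protocol amendment is needed. The cost is SAP wording and derivation code, drawing on the dosing-change and final-dose eCRF entries (Protocol A 1.5 and A 1.6) and the accountability log (Protocol A 1.3). No new data collection is expected, but first confirm that the eCRF lets a directed stop be dated and told apart from a subject's own decision. The downside is some extra derivation work and about one dose of ambiguity at the stop date.

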--	--

	
tests (chemistry, hematology) and urine samples will be taken for urinalysis and a UPT (for WOCBP). Subject will be reminded to continue to take 1 tablet twice daily until the next clinic visit. AEs will be recorded. The subject will be scheduled for the next visit, as appropriate.
 
Visit 6 (Day 85 ± 3): Week 12/End of Treatment [EOT]. One day prior to the visit, the site staff will contact the subject to remind them to note the time of dosing on the Subject Instruction Sheet if the subject chooses to take the morning dose of test article on the day of their clinic visit at home and to inform them that if the subject chooses to take the morning dose of test article in the clinic, the subject will need to remain in the clinic for 1 hour after dosing.
 
On the day of the visit, the subject will return to the clinic and be queried for any changes in health status since the previous visit, including concomitant medications and concurrent procedures/therapies. Vital signs will be measured. Subject evaluation (PGIC) will be performed by the subject and clinical evaluations (IGA first, then BSA and PASI) will be performed by the investigator. A targeted physical examination based on subject symptoms and an ECG will be performed. Non-invasive skin samples will be collected from non-lesional (perilesional) and lesional skin (same areas collected at baseline). Test article accountability will be documented and all test articles will be collected. Subjects who did not take their morning dose at home will take the morning dose of test article under supervision of study staff and will wait 1 hour before blood sample collection. Time of dosing will be recorded. Blood samples will be taken for biomarker analysis and clinical laboratory tests (chemistry, hematology) and urine samples will be taken for urinalysis and a UPT (for WOCBP). AEs will be recorded. The subject will be scheduled for the End of Study (EOS) phone call follow-up visit 3 days after this visit.
 
Visit 7 (3 days after EOT Visit): EOS. The investigator or designee will call and query the subject for any changes in health status since the previous visit, including concomitant medications and concurrent procedures/therapies, and document any AEs. The subject will exit the study.

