### **6.2 Instructions for Use and Administration**

Subject kits will contain bottles containing tablets of test article. The first dose will be taken at the clinic on Day 1. Note: If subject's Day 1 visit is in the evening (i.e., later in the day), and the subject is unlikely to have at least an 8-hour separation between the dose taken at the clinic and the second Day 1 dose, then the dose taken at the clinic will be considered their evening dose and the subject will not dose again until the following morning. Subjects will be instructed to take 1 tablet by mouth twice daily for 12 weeks, once in the morning and once in the evening, with at least 8 hours and preferably 12 hours between doses. Each subject will be provided with a Subject Instruction Sheet providing further dosing details (see Appendix 2).

**For Visit 4**, the morning dose of test article may be taken by the subject at home or may be taken at the site under supervision of the site staff. One day prior to the visit, the site staff will contact the subject to remind them that if the subject chooses to take the morning dose of test article at home on the day of their clinic visit, the subject should: 1) take the morning dose of test article approximately 2 hours prior to the study visit AND 2) note the time of dosing on the Subject Instruction Sheet. Subject will also be informed that if the subject chooses to take the morning dose of test article in the clinic, the subject will need to remain in the clinic for 2 hours after dosing. Time of dosing will be recorded, such that time (in minutes) from test article dosing to blood draw for blood biomarker analysis and urine draw for drug metabolism analysis can be calculated.

**For Visit 5 and Visit 6**, the morning dose of test article may be taken by the subject at home or may be taken at the site under supervision of the site staff. One day prior to the visit, the site staff will contact the subject to remind them to note the time of dosing in the Subject Instruction Sheet if the subject chooses to take the morning dose of test article on the day of their clinic visit at home and to inform them that if the subject chooses to take the morning dose of test article in the clinic, the subject will need to remain in the clinic for 1 hour after dosing. Time of dosing will be recorded, such that time (in minutes) from test article dosing to blood draw for blood biomarker analysis can be calculated.

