#### **17.3.3.2 Dosing Compliance**

Descriptive statistics will be used to summarize the total number of doses for the Safety population. Subjects who take at least 80% of the expected total number of doses and have no other evidence of material dosing non-compliance will be considered to be compliant with test article dosing.

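### SAP 8.6.5 labels a fully adherent subject non-compliant if Protocol 14.3 ends dosing by Day 67 or suspends it for about 17 days

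*SAP*

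**What the plan says.** SAP 8.6.5 computes compliance as 100 times reported doses over expected doses. Reported doses are tablets dispensed minus tablets returned. For the denominator, "the expected number of doses will be 168 (or 167 for subjects for whom only the evening dose (after 4PM) is taken" on Day 1. A subject at 80% or more, with no other sign of material non-compliance, is classed as compliant, and "The number and percent of compliant subjects will be presented". The only other special case is a subject who returns no bottles, whose compliance is unknown.

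Protocol 17.3.3.2 has the same threshold ("Subjects who take at least 80% of the expected total number of doses") but puts no number on expected doses. The fixed count therefore comes from the SAP alone.

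Protocol 14.3 makes some interruptions mandatory: "Subjects will be discontinued from dosing, but will continue to be followed in the trial, if any of the following occurs". For an eGFR of 50 mL/min/1.73 m² or less, "Dosing will be suspended until eGFR exceeds 50" on two consecutive measurements, and no maximum length is given. Protocol A 1.5 also lets the investigator modify dosing after discussion with the Medical Monitor. Protocol A 1.6 records the first and final dose dates, and departures from the specified dosing, on eCRFs. Nothing in SAP 8.6.5 uses those records, and SAP section 9 lists no changes to the planned analysis.

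**The concern.** Doses that the protocol forbids are counted as doses that the subject missed. Both documents describe the trial as primarily one of safety and tolerability, so a safety stop is an outcome of interest. Protocol 13.2 lists adverse events and non-compliance with study drug as separate reasons for withdrawal, yet the flag in SAP 8.6.5 can merge them. A reader of the compliance table could take a subject who followed every instruction, including the instruction to stop, for one who did not take the drug as directed. With about 10 subjects, one such case visibly changes the reported percentage.

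**Working it through.** **1. The plan's own figure.** 12 weeks × 7 days × 2 doses = 168. An evening start removes one dose: 168 − 1 = 167. Both agree with SAP 8.6.5.

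**2. Doses needed at 80%.** 0.80 × 168 = 134.4, so 135 are needed. 0.80 × 167 = 133.6, so 134 are needed. Either way at most 33 doses can be missed.

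**3. Required stop, every permitted dose taken.** If the last full dosing day is d, doses taken are 2d, or 2d − 1 for an evening start.

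| Dosing ends after | Doses/168 | Evening start, doses/167 | Label |
|---|---|---|---|
| Day 28 | 56 = 33.3% | 55 = 32.9% | non-compliant |
| Day 56 | 112 = 66.7% | 111 = 66.5% | non-compliant |
| Day 67 | 134 = 79.8% | 133 = 79.6% | non-compliant |
| Day 68, morning dose | 135 = 80.4% | 134 = 80.2% | compliant |
| Day 68 | 136 = 81.0% | 135 = 80.8% | compliant |

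Days 28 and 56 are the days before the nominal Visits 4 and 5, when laboratory tests and ECGs are scheduled.

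**4. Required suspension, every permitted dose taken.** A pause of p full days removes 2p doses. The number of permitted doses depends on Visit 6 (Day 85 ± 3), because the synopsis keeps subjects on drug from visit to visit: "Subject will be reminded to continue to take 1 tablet twice daily until the next clinic visit". It also depends on whether that morning's dose is in the tablet count. For a morning start:

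| Visit 6 | Permitted doses | Longest pause still compliant | Shortest pause labelled non-compliant |
|---|---|---|---|
| Day 82, without morning dose | 81 × 2 = 162 | 13 days: 136/168 = 81.0% | 14 days: 134/168 = 79.8% |
| Day 85, without | 84 × 2 = 168 | 16 days: 136/168 = 81.0% | 17 days: 134/168 = 79.8% |
| Day 85, with | 169 | 17 days: 135/168 = 80.4% | 18 days: 133/168 = 79.2% |
| Day 88, with | 87 × 2 + 1 = 175 | 20 days: 135/168 = 80.4% | 21 days: 133/168 = 79.2% |

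An evening start gives the same thresholds.

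**5. What the flag can tell apart.** Suppose drug is stopped after 56 permitted doses. A subject who took all 56 scores 56/168 = 33.3%, and one who took 40 scores 40/168 = 23.8%. Both are non-compliant. Against permitted doses they score 56/56 = 100% and 40/56 = 71.4%, and the flag separates them.

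**6. Effect of a permitted-dose denominator.** The subject stopped after Day 56 moves from 112/168 = 66.7% to 112/112 = 100%.

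**7. Weight of one subject.** 1/10 = 10 percentage points in the percentage compliant.

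**The case against.** The strongest reply is that this is a convention, openly stated. SAP 8.6.5 defines compliance as a percentage of the planned 12-week course, and that is a coherent measure. The protocol leaves the expected number undefined, so the SAP contradicts nothing by filling it in. Compliance also decides nothing: Safety is the only population (SAP 8.2.1) and no endpoint uses the flag. In a trial this small the reason for a low figure can be read from disposition (SAP 8.5), the exposure categories (SAP 8.8.1), the adverse event listings (SAP 8.8.3) and the subject listings (SAP 8.1). A long pause may also be rare. Entry requires an eGFR of at least 90, apart from near-limit cases approved by the Medical Monitor, and Phase 1 reported no interruption or discontinuation of drug, though multiple dosing there lasted only 10 days.

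Those limits stand, and they set the size of the point. They do not remove it. Percentage of planned course measures exposure, which SAP 8.8.1 already summarises, whereas 8.6.5 uses it to label a subject's compliance.

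A reader might infer four stronger things that the documents do not support:

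- **That the SAP contradicts itself, because 167 already drops a dose the protocol disallows.** Protocol 6.2 does say that after a late first dose "the subject will not dose again until the following morning". But 167 is the planned count for that start, known on Day 1. It is not a later deduction for withheld drug.
- **That a pregnancy-test hold has the same effect.** Under Protocol 14.6, "the test article must be withheld until the results of laboratory pregnancy testing are available". Nothing shows that this wait could approach 14 days.
- **That SAP 8.6.5 hides all differences among stopped subjects.** Only the yes/no flag does. The section also summarises percentage compliance, where 33% and 24% remain distinct.
- **That efficacy or safety results are affected.** None depends on the flag.

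**Conclusion.** The point holds and is minor. Under SAP 8.6.5 as written, a subject who takes every permitted dose is labelled non-compliant if a Protocol 14.3 stop makes the last dose fall on Day 67 or earlier. The same happens after a suspension of about 17 full days, or 14 to 21 across the Visit 6 window. Later stops and shorter pauses do not trigger it. The consequence is a misleading label and a shift of 10 percentage points per affected subject at N=10.

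This rests on three assumptions: the tablet count is accurate, the subject takes exactly the permitted doses, and SAP 8.6.5 is applied literally. The documents give no expected frequency of stopping-rule events, so the number of subjects affected cannot be estimated and may be zero.

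**What to change.** Amend SAP 8.6.5 so that, for the 80% classification, expected doses are those scheduled from the first dose to the date on which a stopping rule or the investigator ended dosing, or otherwise to end of treatment. Subtract doses falling in any protocol-required or investigator-directed interruption or reduction recorded on the dosing-change eCRF (Protocol A 1.5, A 1.6). Keep the percentage of the planned 168 or 167 doses as a second summary row, so that low exposure stays visible.

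Investigator-directed changes need to be included. If only Protocol 14.3 stops were subtracted, a subject whom the investigator took off drug or gave a drug holiday for poor tolerance would still be called non-compliant.

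The cost is a short addition to the SAP, one extra row, and a derivation of the permitted dosing period from dose dates, dosing-change records, and adverse event and disposition records. Protocol A 1.6 does not promise a coded reason for each dosing change, so some cases may need to be settled from those other records. That should be done by a rule written before database lock. No protocol amendment is needed.
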